### 8.0

#### **Objectives and Justifications**

#### 8.1 Summary of the study using lay language (200 words or less):

The Pathways Collaborative is the first attempt to implement supportive (palliative) kidney care at multiple sites in the United States. While supportive kidney care is growing in other countries, notably Canada, Australia, and Great Britain, it is not yet known how to integrate it into the unique nephrology environment in the United States. In Phase 1 of Pathways (completed), we developed an evidence-based change packet of 14 best practices for integrating supportive care practices into the continuum of care for patients with end stage renal disease (ESRD). In Phase 2 (described in this application), we will conduct a learning collaborative to help up to 15 dialysis centers and associated CKD practices implement these best practices. The learning collaborative is based on the IHI Collaborative Model for Achieving Breakthrough Improvement. This model is a tested systematic approach to quality improvement designed to help organizations close the gap between current and future practice based on evidence-based best practices. [i]

The Pathways Project faculty will work with up to 15 change teams at dialysis centers and associated CKD practices to create a system to identify seriously ill patients with kidney disease; conduct conversations with them so that their values, preferences, and goals for current and future medical treatment are known and respected; assess and address patients' physical, psychological and spiritual needs; and coordinate care throughout the healthcare system so patients receive only the care they want in settings in which they wish to be.

[i] Nadeem E, Olin SS, Hill LC, Hoagwood KE, Horwitz SM. Understanding the components of quality improvement collaboratives: A systematic literature review. *Milbank Q*. 2013;91(2):354-394. doi:http://dx.doi.org/10.1111/milq.12016.

[ii] Wells S, Tamir O, Gray J, et al. Are quality improvement collaboratives effective? A systematic review. BMJ Quality and Safety. 21 October 2017. doi. 10.1136/bmjqs-2017-006926

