#### Aim 3: Develop strategy for dissemination

In fall 2020, the Pathways Project Advisory Committee will develop a strategy to disseminate the revised change package and results of the Collaborative. The dissemination strategy will include outreach to three audiences based on the outcomes of the Pathways Project: 1) the professional and scientific community through presentations at national meetings and articles in peer-reviewed journals; 2) the large dialysis organizations and those who oversee quality of dialysis care including the Forum of ESRD Networks, the individual networks, and the American Health Quality Association; and 3) policy makers including members of Congress and CMS to advocate for changes to improve patient-centered care for patients with kidney disease.

To achieve these aims we will employ three primary tactics:

- 1) The IHI Breakthrough Collaborative Model The Collaborative Model is the primary intervention for this project. It has been used to foster successful change adoption in numerous settings with a variety of health problems.
- 2) Integrated payment models. Integrated payment models realign financial incentives to create a fertile field for uptake of innovations in patient- and family-centered care in the kidney care continuum. Several of the sites participate in the ESCO Model (ESRD Seamless Care Organizations) which is a pilot program being conducted by CMS to test value-based payment models for dialysis care. At least four of the participating dialysis centers are part of the ESCO demonstration. Three centers (at [REDACTED], ) are part of a similar private initiative to provide an integrated care model for ESRD patients. The site within the Veterans Administration also works within the financial system of the VA, which is a budget based model, rather than service reimbursement model.
- 3) The Pathways Change Package Provides an evidence-based set of changes and tools collated from the research literature and experiences and efforts of exemplars and organizations that have already successfully adopted supportive care best practices and shown positive outcomes.

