# 8.4 How will the data be analyzed to answer the research question? Briefly describe the data analysis procedures (e.g., statistical tests, thematic analysis, factors to be compared):

Briefly describe statistical tests, thematic analysis, and the factors to be compared.

Univariate and bivariate statistics will be used to analyze outcomes. Differences between categorical variables will be analyzed with the chi-square test and between continuous variables with the t-test. Trends over time in utilization measures will be analyzed with ANOVA.

To improve the efficiency of the design, given existing limitations, the "post" intervention sample will be matched to the pre-sample in term of cluster size and pre-treatment variables that affect the outcomes of importance.

The effect of the intervention will be measured as the difference between matched clusters (post intervention minus pre-intervention) in outcome changes over the 18-month study period from pre-intervention to post-intervention. Negative differences will indicate lower outcomes post-intervention, adjusted for baseline measures. A one-sample two sided t test with corresponding confidence interval will be used to determine whether the mean difference as calculated over all matched pairs is statistically different from zero. A nonparametric permutation test will also be used with an exact p-value. We will follow the same approach for secondary outcomes on which we have appropriate pre-intervention data. To adjust the mean rate difference in (the primary outcome) between groups for variables that show some residual imbalance after the post-intervention cluster pair-matching, a multiple linear regression model will be used, with the difference between matched clusters within dialysis centers as the dependent variable and variables with pre-intervention differences between matched clusters as the independent variables. Adjusted inferences for the effect of the intervention will be estimated by calculating the intercept of the resulting regression equation and comparing it to its estimated standard error.

Donner A, Klar N: Design and Analysis of Cluster Randomization Trials in Health Research. New York: Wiley; 2000. Section 6.3.3.	

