- 4. The subjects who give verbal consent will be asked to complete the surveys at the intervals specified in the measures spreadsheet. The Kidney Supportive Nephrology Care Implementation Quotient and the NoMAD implementation tool only need to be completed twice. The Institute for Healthcare Improvement single-item measure needs to be completed monthly (but only by the head of the change team).

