# \*If excluding a population or group that may benefit from the research, please provide justification:

All patients will potentially receive the impact of changes in care processes implemented by the dialysis and CKD centers. However, only patients who are cognitively able and English or Spanish speaking will be surveyed by phone. We do not have the budget to translate the survey instruments nor hire survey administrators fluent in languages other than English and Spanish.

10.8 Special populations to be involved in the research:	

 
✓ Employees
 
Students
 
Educationally Disadvantaged
 
Economically Disadvantaged
 
Mentally Ill
 
Decisionally-Impaired
 
Illiterate
 
✓ Non-English speaking
 
Research conducted internationally
 
Other
 
	
For any population listed above, please explain why the population is necessary and explain additional steps that will be taken to protect the subjects:	
Dialysis center and/or CKD practice patients: patients are the only ones who can report on whether communication is effective from their point of view. Therefore a direct survey of patients is the only way to obtain patient assessment of whether communication practices have improved as a result of the project. When the survey is explained to them, they will be assured that their care will not change regardless of whether they participate in the survey or not. Also, when the survey administrator introduces the survey, the administrator will remind them that they can skip any questions or stop the survey at any time.	
Non-English speaking: Spanish-speaking patients are a significant proportion of the patients served by the participating dialysis and CKD clinics. At some sites, they are a third or more of patients served. Excluding Spanish-speaking patients would make it more difficult to generalize to this population, and possibly limit their access to the care improvements developed by this project. To protect these patients we are hiring an interviewer who is fluent in Spanish to conduct the consent process and patient interview. The Spanish translation of the survey will be prepared by a professional translator for the portions that are not already available as Spanish translations of validated scales. We will also have an arrangement with a telephone interpreter service available to use if any participating patient has concerns and wants to talk with members of the research team.	

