# B. Staff perception of organizational competence in delivering supportive kidney care - Kidney Supportive Care Implementation Quotient (KSC-IQ on-line survey)

the emotional and ethical distress which some staff perceive when providing care that is misaligned with patient goals.	
C. Staff change team perception of integration of new practices - NOMAD survey (online)  Staff will be helping their organization improve supportive care. This MAY improve working conditions by reducing the emotional and ethical distress which some staff perceive when providing care that is misaligned with patient goals.	
D. Facility level monthly report of aggregate utilization statistics  By measuring improvement in quality indicators, dialysis center and CKD practice will see progress in better communication and better and more consistently delivery of supportive kidney care. This improvement in care will benefit patients. It may also reduce moral distress for staff who experience distress from delivering care that does not align with patient goals.	
E. Seriously ill patients demographic and utilization statistics  No direct benefit to current patients. By measuring demographics and utilization characteristics of entire seriously ill group at baseline and follow-up to allow comparison between patients who are interviewed and those who are not, the validity of the research is strengthened. This makes it more likely that the final results will be interpretable, and that what is learned in the implementation of the project could in the future be used to improve care for similar seriously ill patients.	
F. MMWD CKD Intervention Tracker  No direct benefit to current patients. The data we collect will be suitable only for descriptive analysis, but will provide information and experience towards future, more systematic efforts, and that what is learned in the implementation of the project could in the future be used to improve care for similar seriously ill patients.	
16.4 Benefits of this research for society:	
If the intervention to implement supportive care in dialysis centers is successful, it will provide a scalable approach to improve dialysis patient care throughout the country.	
16.5 Is any deception or incomplete disclosure (withholding of complete information) required for the validity of this study?	
O yes ⊙ No	
16.6 Is there a data and safety monitoring plan or board (DSMB) for this study?	

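### Section 8.4 labels an uncontrolled before/after change as the effect of the intervention, although every center receives the collaborative and nothing separates its effect from a change common to all centers

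*Combined protocol and SAP*

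**What the plan says.** Section 8.1 sets out the intervention: "we will conduct a learning collaborative to help up to 15 dialysis centers and associated CKD practices implement these best practices". No section describes a center that does not take part or that starts later. The justification under section 10.7 adds that exposure inside a center is general: "All patients will potentially receive the impact of changes in care processes implemented by the dialysis and CKD centers".

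Section 9.1 A plans one patient survey in a baseline period and one in a separate cohort after the 18 months of activity, with 360 patients per wave across 15 sites.

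Section 8.4 defines the estimate: "The effect of the intervention will be measured as the difference between matched clusters (post intervention minus pre-intervention) in outcome changes". The pairs are formed over time within a center. The section says that "the 'post' intervention sample will be matched to the pre-sample in term of cluster size and pre-treatment variables", and its regression is run "with the difference between matched clusters within dialysis centers as the dependent variable". The mean difference over pairs is tested against zero with a two-sided one-sample t test and with a permutation test described as exact. The regression intercept is presented as the adjusted effect of the intervention.

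The hypothesis in section 8.2 is causal: the collaborative approach is expected to lead to improvement. Section 16.4 looks ahead to use elsewhere: "If the intervention to implement supportive care in dialysis centers is successful, it will provide a scalable approach".

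**The concern.** Within-pair differences measure an intervention effect when one member of each pair is treated and the other is not. Here both members are the same center at two times, and every center is treated in between. Section 8.4 speaks of a difference between groups and of a difference in outcome changes. That reads like a difference in differences, but each center has only one series, so there is no second change to subtract.

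A significant result would therefore be reported as the collaborative's effect if practice, staffing, documentation or expectations had shifted across the centers for any other reason. A drift in the opposite direction could hide a real benefit. Section 8.2 plans dissemination to dialysis organizations and policy makers, so the label on this estimate determines what the study will be said to have shown.

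**Working it through.** **No plan figure to reproduce.** The documents contain no power calculation, alpha, effect size or SD.

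**What the planned quantities estimate.** Let d_i be center i's post-minus-pre difference, θ the collaborative's mean effect, and δ the change common to all centers that measured covariates do not explain. Then

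d_i = θ + δ + (part explained by measured covariate differences) + error.

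- The mean of d_i estimates θ + δ plus the case-mix part.
- Matching and regression can remove the case-mix part. The intercept then estimates θ + δ.
- Neither gives θ unless δ = 0, and nothing in the plan estimates δ.

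**Inputs from the documents.** 15 centers; 360 / 15 = 24 patients per center per wave; a two-sided one-sample t test, so 14 df.

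**Assumptions not in the documents.** Alpha 0.05; binary outcome with p0 = 0.40 at baseline; θ = 0; δ = 5 or 10 points; SD of center-level drift τ from 0 to 0.10.

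**Formulas.** With p1 = p0 + δ:

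- Var(d) = [p0(1 − p0) + p1(1 − p1)] / 24 + τ²
- SE = √(Var(d) / 15), noncentrality = δ / SE
- Reject when |t| > 2.145

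| δ | τ | Var(d) | SE | Noncentrality | P(reject), noncentral t | P(reject), 20,000 simulations |
|---|---|---|---|---|---|---|
| 5 points | 0 | (0.2400 + 0.2475)/24 = 0.0203 | 0.0368 | 1.36 | 24.5% | 24.9% |
| 5 points | 0.10 | 0.0203 + 0.0100 = 0.0303 | 0.0450 | 1.11 | 17.9% | 18.2% |
| 10 points | 0 | (0.2400 + 0.2500)/24 = 0.0204 | 0.0369 | 2.71 | 71.3% | 71.6% |
| 10 points | 0.10 | 0.0204 + 0.0100 = 0.0304 | 0.0450 | 2.22 | 54.3% | 54.7% |

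With δ = 0 the simulated rejection rate is about 5%, so the test is sound for its own null. In the simulations the mean estimate equals the drift put in: 0.05 for 5 points and 0.10 for 10 points.

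**Sensitivity.** With a baseline of 30% or 50%, and a center-by-period variance share of 0 to 0.05 of p(1 − p), the noncentral t gives 14% to 27% at 5 points and 41% to 75% at 10 points.

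**Threshold.** An observed mean difference of 2.145/√15 = 0.554 SD of the center differences gives p = 0.05. With SDs of √0.0203 = 0.142 and √0.0303 = 0.174, that is about 7.9 to 9.6 points.

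**Permutation test.** At baseline 40% and variance share 0.02, the sign-flip test rejects 4.0%, 17.2% and 49.8% of the time for drifts of 0, 5 and 10 points. The t test gives 4.8%, 18.8% and 55.2% in the same setting. Flipping signs is justified by random assignment of the two labels or by symmetry about zero. Calendar order was not assigned at random, and a common drift moves the center of symmetry away from zero.

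**The case against.** The strongest reply is that this is a limitation of the design and not a wrong analysis. The study is a single-group quality-improvement collaborative, section 8.7 says it is not a clinical trial, and section 8.4 answers a form that asks for a brief description. Much of this stands. A before/after design is a legitimate choice, and the t test validly tests no change. The passing mention of existing limitations in 8.4 does not settle the matter, because it says nothing about trend or attribution.

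Second, the rejection rates are in effect a power curve for detecting a real change, under assumed drifts. That is correct. They show what follows if drift occurs, not that it is likely.

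Third, the plan is not silent on time. It has matching and regression, an ANOVA of utilization trends, 18 months of monthly reports, and a staff survey on integration of the new practices after the first and third learning periods. A reader might infer that any secular change at all passes into the estimate, or that nothing in the plan bears on attribution. Both go too far. Measured case mix can be adjusted for, and the trend data are relevant though weak. The monthly reports, however, cover only the collaborative period, and 8.4 does not link the ANOVA to the effect estimate.

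A reader might also infer that integrated payment is a competing cause, since section 8.2 says "At least four of the participating dialysis centers are part of the ESCO demonstration" and mentions three centers in a private initiative and one Veterans Administration site. The documents do not support that. They do not say that payment arrangements changed between the waves, and a stable center feature cancels in a within-center difference unless its influence changes. Adding the groups to at least eight centers assumes no overlap, which is not stated.

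Finally, the title of the cited text concerns cluster randomization. What its cited section says cannot be checked from these documents, so nothing here rests on it.

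**Conclusion.** The concern holds for the label and the inference, not for the arithmetic of the test. Section 8.4 should not call the post-minus-pre difference, or its regression intercept, the effect of the intervention, because both contain any common change that measured case mix does not explain. If the collaborative did nothing, a 5-point common drift would be declared significant about 18% to 25% of the time and a 10-point drift about 55% to 71%, against 5% with no drift. These figures rest on the assumed 40% outcome, alpha and drift SD, and on 15 centers with 24 patients each. The structural conclusion does not depend on them.

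It does not follow that the t test is invalid, that drift has been shown, or that the collaborative has no effect.

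**What to change.** In section 8.4:

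1. Open the defining sentence with: *The change from baseline to follow-up will be measured as*. Make the same substitution in the sentence on adjusted inference, so that the intercept is described as an adjusted change.
2. Add: *The t test and permutation p-values test the hypothesis of no change over the period. Without a comparator, the change cannot be attributed to the collaborative alone.* Keep the claims in reports and dissemination within that limit.
3. Optionally, report the mean change by ESCO status, which Instrument E already records, and its association with implementation scores. Mark both as descriptive and exploratory. They are not evidence of attribution. One candidate score is a self-rating by an involved person: "The Institute for Healthcare Improvement single-item measure needs to be completed monthly (but only by the head of the change team". Centers that implement more may differ in other ways, and a slope over 15 centers is imprecise, with about 48% power at a correlation of 0.5.

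The cost is a few sentences and, if wanted, two small summaries from data already planned. The downside is a weaker stated claim. The change should be made before follow-up results are seen.

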#### A. Patient-reported outcomes (telephone survey)

The steps in the procedure for the subjects who are patients are as follows:

- 1. The subjects (ESRD patients), who are being treated at participating dialysis centers and CKD practices and are identified as "seriously ill" by clinic staff using the screening tool, will form the population from which patients will be selected. We plan to survey 360 patients across the 15 participating sites during the baseline period. We will select a separate cohort of another 360 patients to interview at the completion of the 18-month learning collaborative.
- 2. Identified subjects will be approached by a member of the dialysis organization or CKD practice. The nature of the study will be explained. If the patient agrees to be contacted to learn more about the study, their contact information will be shared with the WVU CTSI and a research coordinator from WVU CTSI will contact the patient to explain the study. If the patient is interested, the interviewer will provide information needed for informed consent and will obtain verbal consent to proceed. A copy of the information provided during verbal consent process will be mailed to patients who consent along with the incentive gift card.
- 3. The subjects who give verbal consent will be interviewed as described in the attached patient questionnaire.
- 4. A "thank you" incentive of a \$25 gift card will be mailed to patients who complete the survey.

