#### E. Patient level demographic and utilization information

This is collected on all patients who are identified as seriously ill, using a validated screening process. At most centers, we expect about 20% of centers at the patient will be identified as seriously ill. We expect 300 patients to be identified at baseline (20% of the 1500 total patients) and another cohort of 300 patients to be identified at follow-up.

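### Does the covariate rule in section 8.4 adjust for nothing, because each center is paired with itself?

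*Combined protocol and SAP*

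**What the plan says.** Section 8.4 sets out a before-and-after comparison at the level of the center. On the follow-up cohort it states: "intervention sample will be matched to the pre-sample in term of cluster size and pre-treatment variables that affect the outcomes of importance". Its effect measure is a difference between matched clusters, post minus pre, "in outcome changes over the 18-month study period from pre-intervention to post-intervention". A two-sided one-sample t test and an exact permutation test are applied to the mean difference over pairs.

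An adjusted analysis follows. It is a linear regression with "the difference between matched clusters within dialysis centers as the dependent variable". Its aim is to adjust for "variables that show some residual imbalance after the post-intervention cluster pair-matching", and its regressors are described as "variables with pre-intervention differences between matched clusters as the independent variables". Inference is by "calculating the intercept of the resulting regression equation and comparing it to its estimated standard error". The section ends by citing a section of a cluster-trial methods text, and its form heading asks for a brief description.

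Three other places bear on the point:

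- Section 9.1 A: "We will select a separate cohort of another 360 patients to interview at the completion of the 18-month learning collaborative".
- Section 10.1 E expects 300 seriously ill patients at baseline and "another cohort of 300 patients to be identified at follow-up".
- Section 9.1 E collects demographic and health-status data in both periods and links them to the survey.

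**The concern.** The documents describe no control group, and the differences are formed within dialysis centers. The natural inference is that a pair is one center before and after the collaborative. Such a pair has a single pre-intervention state, so a covariate defined as a pre-intervention difference between its two members is zero by construction. The adjustment would then do nothing.

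That would matter in this design. The two cohorts are selected separately, 18 months apart, and staff judgment decides who counts as seriously ill. A shift in who is identified and who answers is a rival explanation for a shift in outcome, and the regression is the only stated step that could remove a measured part of it.

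Three smaller points sit alongside. The text gives no reference distribution for the intercept. The wording about outcome changes seems to call for a second change, and none exists. It is also unclear whether patients are selected to match or only centers are paired. Selecting patients could cost precision when about 300 are expected per wave against a survey target of 360.

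**Working it through.** **Inputs from the documents.** Up to 15 centers (section 8.1). Survey plan 360/15 = 24 patients per center per wave (9.1 A). Expected seriously ill 300/15 = 20 per center per wave (10.1 E). Section 8.4 gives no SD, intracluster correlation, effect size or significance level, so there is no planned figure to reproduce. Every other input below is an assumption.

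**What each coding does to the intercept.** Let D = post mean minus pre mean of the outcome in a center, X the center mean of a patient characteristic, and fit D = a + bZ + error over 15 centers.

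- Strict reading: Z = 0 in every center. The estimate of a is mean(D), on 14 df. This identity needs no assumed number.
- Imbalance reading: Z = X(post) − X(pre), uncentered. The estimate of a is mean(D) − b·mean(Z), the change at zero imbalance, on 15 − 2 = 13 df.
- Centered Z: the estimate of a is mean(D) again, so nothing is adjusted.
- Raw baseline level: a is extrapolated to X = 0.

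**First simulation.** Assumed: 24 patients per center per wave, age with patient SD 12 and center-mean SD 4 around 65 years, slope 0.03 outcome SD per year, residual SD 1, two-sided 5% level, true effect 0, cohort age shift 3 years, 20,000 runs. Checks by hand: bias without adjustment = 0.03 × 3 = 0.09; SE = √[2(0.03²·144/24 + 1/24)/15] = √(0.0941/15) = 0.079.

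| Coding | Mean intercept | Mean SE | False rejection |
|---|---|---|---|
| Unadjusted, or strict zero column | 0.09 | 0.078 | 18.4% |
| Post minus pre, uncentered | 0.00 | 0.102 | 5.0% |
| Post minus pre, centered | 0.09 | 0.073 | 21.5% |
| Baseline level, centered | 0.09 | 0.077 | 18.7% |
| Baseline level, raw | 0.62 | 1.172 | 8.3% |

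With no shift, the unadjusted test rejects in 5.3% of runs and the uncentered difference in 5.0%.

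**Second simulation.** Assumed: 20 patients per center per wave, one characteristic explaining 10% of patient variance, variance of true center changes 0.05, between-center SD of the shift 0.2, no true effect. Under the strict reading, false rejection is 6%, 9%, 14% and 30% at shifts of 0.1, 0.2, 0.3 and 0.5 SD. The uncentered difference stays at about 5% on 13 df; a 1.96 cut-off would give about 7%. Over shifts of 0.3 to 0.5 SD with varied inputs, the strict reading gives 8% to 69%. The top figure is the extreme corner: shift 0.5, 20% explained, no center variance, 20 patients.

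**Price of adjusting.** The intercept's SE grows by √(1 + 15k²/14), where k is the mean shift divided by the SD of the center differences in X. That SD is √(2/20 + 0.2²) = 0.374. Shifts of 0.3 and 0.5 give k = 0.80 and 1.34, and factors of 1.30 and 1.71. The unadjusted SD of the estimate is 0.101; simulated values with adjustment are 0.132 and 0.176.

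**Price of patient matching, if it were done.** Under exact 1:1 matching within center on one or two three-level variables with equal cells, the kept fraction f is 82% or 65% at n = 20, and 77% or 56% at n = 12. The SE factor √[(2/(nf) + v)/(2/n + v)] runs from 1.10 to 1.34 with center-change variance v = 0, and from 1.07 to 1.27 with v = 0.05. The documents do not mention such a scheme.

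**The wording side by side.** The first half of the sentence names imbalance left after matching the post cohort to the pre cohort. The preceding paragraph matches on pre-treatment variables. Read together, pre-intervention describes the kind of variable (a patient characteristic the intervention did not produce), not a second measurement date. The use of the intercept as the effect settles the coding: zero on the covariate must mean no imbalance, so the covariate is the imbalance itself, uncentered.

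**The case for a change.** The strongest case for a change is that the estimate depends on the coding and the text does not state it. Section 8.4 also speaks of adjustment for baseline measures, which could send an analyst to baseline levels. In the first table only one coding gives an adjusted effect with the right error rate. The data needed are already collected, so a clarification would take a few sentences.

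Part of this stands. Writing down the coding, the variables and the level of matching would be tidy, and unnamed covariates leave some freedom of choice with at most 15 pairs. But the wrong codings do not survive use. A zero column is visibly useless. A centered covariate returns the unadjusted mean exactly. A raw level gives an SE about 15 times larger (1.172/0.078). Comparing a linear-regression intercept with its standard error ordinarily means a t test on residual df; nothing in the section suggests 1.96. The cited methods text may also cover these details, though that cannot be checked from the documents.

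On matching, section 8.4 does place the pairing at the cluster, within centers. Whether patients are also selected is open. Section 12.2 has staff approach each eligible patient, but only for permission to be contacted, and section 9.1 A speaks of selecting patients from the seriously ill. A loss of completed interviews is therefore possible but not established.

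A rule of one or two fixed covariates and no patient matching goes beyond wording. Statisticians would differ on it, because the adjustment costs precision and removes neither an unmeasured shift nor a secular trend.

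**Conclusion.** The concern holds only for one phrase taken strictly in time, and only if each center is its own pair, which is a strong inference and not a stated rule. The full sentence supplies a rule that works, and an analyst would apply it: uncentered post-minus-pre differences in patient characteristics, with the intercept tested on residual df. On that reading false rejection is about 5% in both simulations. The 18.4%, and the 6% to 69% across the second set, belong to a reading the plan does not require and rest on assumed shifts, slopes and variances.

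The reference to outcome changes is a redundancy: the parenthesis beside it already defines the difference as post minus pre, and no result depends on it. The choice of variables and the question of patient matching are trade-offs. Under the second set of assumptions, adjustment raises the SD of the estimate from 0.101 to 0.132 or 0.176 at shifts of 0.3 or 0.5 SD. The t test and the permutation test are unaffected by the covariate wording. No change is needed.
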